4.3. Justification for Dose

Mepolizumab 100 mg SC every 4 weeks is as per approved dose (Prescribing Information) by Indian Regulatory Authorities.

4.4. End of Study Visit

A participant is considered to have completed study treatment if he/she has received a dose of mepolizumab at Visit 7 (Week 20) of the study.

A participant is considered to have completed the study if he/she has completed the 24 week treatment period of the study including the end of study visit.

The end of the study is defined as the date of the last visit of the last participant in the study.

5. STUDY POPULATION

Prospective approval of protocol deviations to recruitment and Treatment Period criteria, also known as protocol waivers or exemptions, is not permitted.

5.1. Inclusion Criteria

Participants are eligible to be included in the study only if all of the following criteria apply:

Age

1. Participant must be ≥ 18 to 65 years of age inclusive, at the time of signing the informed consent.

Type of Participant and Disease Characteristics

- 2. Asthma: Evidence of asthma as documented by either:
 - Airway reversibility (FEV1≥12% and 200 ml) demonstrated at Visit 1 (screening), or Visit 2 (Week 0) OR documented in the previous 12 months OR
 - Airway hyper-responsiveness (methacholine: PC20 of <8mg/mL or histamine: PD20 of $<7.8~\mu$ mol; mannitol: decrease in FEV1 as per the labelled product instructions) documented in the 12 months prior to Visit 2 (Week 0) OR
 - Airflow variability in clinic FEV1 ≥20% between two consecutive clinic visits documented in the 12 months prior to Visit 2 (FEV1 recorded during an exacerbation should not be considered for this criteria) OR
 - Airflow variability as indicated by >20% diurnal variability in peak flow observed on 3 or more days during the optimisation period
- 3. Participants with Eosinophilic asthma: prior documentation of eosinophilic asthma or high likelihood of eosinophilic asthma as
 - FEV1: Persistent airflow obstruction as indicated by:
 - For participants \geq 18 years of age at Visit 1 (screening), or Visit 2 (Week 0), a prebronchodilator FEV1 <80% predicted
 - For predicted FEV1 values NHANES III values will be used and adjustments to these values will be made for race [Hankinson, 1999].
- 4. Eosinophilic Phenotype: Airway inflammation characterized as eosinophilic in nature as indicated by one of the following characteristics:
 - a. An elevated peripheral blood eosinophil level of ≥300 cells/µL that is related to asthma within the previous 12 months prior to Visit 2 (Week 0)

OR

b. Peripheral baseline eosinophil level ≥150 cells/μL between Visit 1 (screening) and Visit 2 (Week 0) that is related to asthma

- 5. Patients eligible for mepolizumab treatment as per independent clinical judgment of treating physician in alignment with local prescribing information.
- 6. Inhaled Corticosteroids: requirement for regular treatment with high dose inhaled corticosteroid in the 6 months prior to Visit 1 (screening).

For 18 years of age and older:

- ICS dose must be ≥880 mcg/day fluticasone propionate (FP) (ex-actuator) or equivalent daily.
- 7. Controller Medication: Current treatment with an additional controller medication for at least 3 months OR having used and failed an additional controller medication for at least 3 successive months during the prior 12 months [e.g., long-acting beta2-agonist (LABA), leukotriene receptor antagonist (LTRA), or theophylline].

Sex

8. Male or eligible female

Contraceptive use by women should be consistent with local regulations regarding the methods of contraception for those participating in clinical studies.

Female Participants:

A female participant is eligible to participate if she is not pregnant or breastfeeding, and at least one of the following conditions applies:

- Is not a woman of childbearing potential (WOCBP)
 OR
- o Is a WOCBP and using a contraceptive method that is highly effective, with a failure rate of <1%, as described in Appendix 4 during the intervention period and for at least 16 weeks after the last dose of study intervention. The investigator should evaluate the effectiveness of the contraceptive method in relationship to the first dose of study intervention.
- A WOCBP must have a negative highly sensitive (Appendix 2) pregnancy test (serum) within 8 weeks before the first dose of study intervention.
- Additional requirements for pregnancy testing during and after study intervention are located in Appendix 2.
- The investigator is responsible for review of medical history, menstrual history, and recent sexual activity to decrease the risk for inclusion of a woman with an early undetected pregnancy

Informed Consent

9. Capable of giving signed informed consent as described in Appendix 1 which includes compliance with the requirements and restrictions listed in the informed consent form (ICF) and in this protocol.

5.2. Exclusion Criteria

Participants are excluded from the study if any of the following criteria apply:

Medical Conditions

- 1. Concurrent Respiratory Disease: Presence of a clinically important lung condition other than asthma. This includes but is not limited to current infection, bronchiectasis, pulmonary fibrosis, bronchopulmonary aspergillosis, or diagnoses of emphysema or chronic bronchitis (chronic obstructive pulmonary disease other than asthma) or a history of lung cancer.
- 2. Malignancy: A current malignancy or previous history of cancer in remission for less than 12 months prior screening (Participants who had localized carcinoma (i.e. basal or squamous cell) of the skin which was resected for cure will not be excluded).
- 3. Liver Disease: Unstable liver disease (as defined by the presence of ascites, encephalopathy, coagulopathy, hypoalbuminemia, oesophageal or gastric varices or persistent jaundice), cirrhosis, and known biliary abnormalities (with the exception of Gilbert's syndrome or asymptomatic gallstones).
- 4. Cardiovascular: Participants who have severe or clinically significant cardiovascular disease uncontrolled with standard treatment. Including but not limited to:
 - known ejection fraction of <30% OR
 - severe heart failure meeting New York Heart Association Class IV (Appendix 5) OR
 - hospitalised in the 12 months prior to Visit 1 (screening) for severe heart failure meeting New York Heart Association Class III (Appendix 5) OR
 - angina diagnosed less than 3 months prior to Visit 1 (screening) or at Visit 1
- 5. Other Concurrent Medical Conditions: Participants who have known, pre-existing, clinically significant endocrine, autoimmune, metabolic, neurological, renal, gastrointestinal, hepatic, haematological or any other system abnormalities that are uncontrolled with standard treatment.
- 6. Eosinophilic Diseases: Participants with other conditions that could lead to elevated eosinophils such as Hypereosinophilic Syndromes, including Churg-Strauss Syndrome, or Eosinophilic Esophaghitis.
- 7. Participants with a known, pre-existing parasitic infestation within 6 months prior to Visit 1 (screening) are also to be excluded.

Prior/Concomitant Therapy

- 8. Omalizumab Use: Participants who have received omalizumab [Xolair] within 130 days of Visit 1 (screening)
- 9. Other Monoclonal Antibodies: Participants who have received any monoclonal antibody (other than Xolair) to treat inflammatory disease within 5 half-lives of Visit 1 (screening)

10. Investigational Medications: Participants who have received treatment with an investigational drug within the past 30 days or five terminal phase half-lives of the drug whichever is longer, prior to Visit 1 (this also includes investigational formulations of marketed products).

Prior/Concurrent Clinical Study Experience

11. Participants who have previously participated in any study of mepolizumab and received Investigational Product (including placebo).

Diagnostic assessments

12. ECG: ECG assessment QTcF > 450msec or QTcF > 480 msec for participants with Bundle Branch Block.

Participants are excluded if an abnormal ECG finding from the 12-lead ECG conducted at Screening (Visit 1) is considered to be clinically significant and would impact the participant's participation during the study, based on the evaluation of the Investigator.

13. Immunodeficiency: A known immunodeficiency (e.g. human immunodeficiency virus – HIV), other than that explained by the use of corticosteroids taken as therapy for asthma

COVID-19 Related Exclusion

14. Participants that have a current active COVID-19 infection, either laboratory confirmed or according to the investigator's medical judgement.

Note: Participants who have confirmed or suspected COVID-19 infection may be rescreened 4 weeks or more after the resolution of the COVID-19 infection and only after written approval from the study Medical Monitor.

15. Participants known to be in contact with active COVID-19 positive individuals within the past 14 days.

Note: Participants may be re-screened 14 days or more following the contact, during which the participant should remain symptom free, and only after written approval from the study Medical Monitor.

Other Exclusions

- 16. Smoking history: Current smokers or former smokers with a smoking history of ≥10 pack years. A former smoker is defined as a participant who quit smoking at least 6 months prior to Visit 1 (screening)
- 17. Hypersensitivity: Participants with a known allergy or intolerance to a monoclonal antibody or biologic.
- 18. Pregnancy: Participants who are pregnant or breastfeeding. Patients should not be enrolled if they plan to become pregnant during the time of study participation.

- 19. Alcohol/Substance Abuse: A history (or suspected history) of alcohol misuse or substance abuse within 2 years prior to Visit 1 (screening).
- 20. Adherence: Participants who have known evidence of lack of adherence to controller medications and/or ability to follow physician's recommendations.

Re-screening of participants will be allowed only upon approval by the medical monitor.

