1. PROTOCOL SUMMARY

1.1. **Synopsis**

Protocol Title: A Phase 4, open-label, single arm, 24-week, study to evaluate the safety and efficacy of Mepolizumab 100 mg SC administered every 4 weeks in Indian participants aged ≥18 years with Severe eosinophilic asthma(PRISM).

Short Title: Phase 4 study of mepolizumab 100 mg SC in Indian participants aged ≥18 years with severe eosinophilic asthma

Rationale:

Indian Regulatory authorities have approved marketing of mepolizumab in India for the treatment of severe eosinophilic asthma based on data from multi-centre, multi-national studies. However, these studies did not include India as a participating country. As part of the approval process, the agency has asked for data to be generated in the Indian population.

Objectives and Endpoints:

Objectives	Endpoints			
Primary				
To evaluate the safety, and tolerability of mepolizumab in participants with severe refractory asthma with elevated eosinophils	 Incidence of on-treatment adverse events (AEs), serious adverse events (SAEs) and adverse events of special interest (AESIs) Summary measure: Counts and percentages for incidence of at least one AE will be summarised overall, by system organ class and by preferred term Population of interest: Severe refractory asthma patients in India with elevated eosinophils			
	A supplementary estimand will be defined using			

[figure not shown]
Objectives	Endpoints
	 identical properties as for the primary estimand (summary measure, population of interest and key intercurrent events), however this supplementary estimand will report all AEs regardless of the discontinuation of study treatment. Endpoints: Incidence of AEs and SAEs Strategy for intercurrent events: Treatment policy strategy will be used for treatment discontinuation. This summary will therefore be inclusive of all on-treatment and post-treatment AEs.
Secondary	

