1.3. Schedule of Activities (SoA)

Table 1 Time and Events Table

Procedure	Pre- Screen	Screenin g	Treatment Period (visit window is ± 7days)			IP Discontinu ation visit	End of study visit	Notes			
Visit		1	2	3	4	5	6	7		8	
Week		-2 to -1	0	4	8	12	16	20	4 weeks post last dose ± 7 days	24 or Early Withd rawal	
Written Informed Consent	X	X									 Pre-screen visit can occur on the same day as the Visit 1 but must be completed prior to starting Visit 1 (screening) procedures. Visit 2 (Week 0) must occur at least one week following Visit 1 (screening) Visit 2 (Week 0) will be considered Baseline
Demography		X								:	
Medical History		X									
Asthma and Exacerbation History (including triggers)		Х									
Asthma Therapy History		X									Therapy history to include a detailed review of prior monoclonal antibodies received for treatment of asthma, including prior investigational anti-IL5 or anti-IL13 preparations.

Procedure	Pre- Screen	Screenin g		Treatment Period (visit window is ± 7days)			IP Discontinu ation visit	End of study visit	Notes		
Visit		1	2	3	4	5	6	7		8	
Week		-2 to -1	0	4	8	12	16	20	4 weeks post last dose ± 7 days	24 or Early Withd rawal	
Oral Corticosteroid Therapy History		X									
Smoking History		X									
Cardiovascular History/risk factors		X									
Parasitic Screening		X									
Inclusion/Exclusion Criteria		х	х								Study inclusion/exclusion criteria should be reviewed at the beginning of visit 2(Week 0). The review should include the results of any lab/safety assessments conducted at Visit 1 (screening).
Treatment Period Criteria			x								
Efficacy Assessments						_		_			
Exacerbation review			х	X	X	х	х	х	X	Х	Number of clinically significant exacerbations (including exacerbations requiring hospitalization, Emergency Department) visits will be evaluated
Spirometry including FEV ₁ , FVC		Х	х		Х		Х		X	Х	

Procedure	Pre- Screen	Screenin g	Treatment l		7days)				IP Discontinu	End of study	Notes
									ation visit	visit	
Visit		1	2	3	4	5	6	7		8	
Week		-2 to -1	0	4	8	12	16	20	4 weeks post last dose ± 7 days	24 or Early Withd rawal	
Maximum Post Bronchodilator Procedure		х	x						х	X	Maximum Post Bronchodilator Procedure is required to complete reversibility testing. If participant does not reverse ≥12% in FEV₁ at Visit 1 (screening), the procedure may be repeated at Visit 2 (Week 0).
OCS dose adjustment review (where applicable)		Х		х	Х	Х	Х	Х			OCS dose adjustment should be reviewed at scheduled in-clinic Visits

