3. OBJECTIVES AND ENDPOINTS

Objectives	Endpoints
Primary	*
To evaluate the safety, and tolerability of mepolizumab in participants with severe refractory asthma with elevated eosinophils	The primary estimand will be defined by the following: Endpoints: Incidence of on-treatment adverse events (AEs), serious adverse events (SAEs) and adverse events of special interest (AESIs)
	 Summary measure: Counts and percentages for incidence of at least one AE will be summarised overall, by system organ class and by preferred term
	 Population of interest: Severe refractory asthma patients in India with elevated eosinophils
	Key intercurrent events:Discontinuation of treatment (for any reason)
	 Strategy for intercurrent events: While on-treatment strategy will be used for treatment discontinuation. This will estimate the percentage of participants experiencing an AE, while receiving treatment. AEs will be defined as on-treatment between the first dose up to and including 28 days following the last dose of mepolizumab.
	A supplementary estimand will be defined using identical properties as for the primary estimand (summary measure, population of interest and key intercurrent events), however this supplementary estimand will report all AEs regardless of the discontinuation of study treatment. Endpoints: Incidence of AEs and SAEs
	 Strategy for intercurrent events: Treatment policy strategy will be used for treatment discontinuation. This summary will therefore be inclusive of all on-treatment and post-treatment AEs.
Secondary	
To evaluate the efficacy of mepolizumab in participants	The following secondary estimand is defined by the following:

Objectives	Endpoints
with severe refractory asthma	Endpoints:
with elevated eosinophils	 Number of clinically significant exacerbations (including exacerbations requiring hospitalization or ED visits) Number of exacerbations requiring hospitalization or ED visits Number of exacerbations requiring hospitalization Summary measure: Rate ratio comparing events/year during the 24-week follow-up period compared to the 12 months prior to screening Population of interest: Severe refractory asthma patients in India with elevated eosinophils Key intercurrent events: Discontinuation of treatment (for any reason)
	 Strategy for intercurrent events: Treatment policy strategy will be used for treatment discontinuation. This will estimate the treatment effect over the 24 week study period regardless of treatment discontinuation.

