6.7. Intervention after the End of the Study

The investigator is responsible for ensuring that consideration has been given to the post-study care of the patient's medical condition. GSK will not supply mepolizumab post study since the mepolizumab will be available commercially. At the end of the study, participants may be prescribed appropriate alternative asthma therapy if needed and as determined by the study Investigator.

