9.4.2. Efficacy Analyses

All efficacy analyses will be performed on the Safety Population.

The study estimands are defined within Section 3 (Objectives and Endpoints). Further details regarding the estimation of each estimand is defined within the table below.

Taking prohibited medication during the treatment period is an important protocol deviation (PD) and will be included in the PD summary. However, this is not considered as an intercurrent event for the estimands defined within this study.

Endpoint	Statistical Analysis Methods
Primary	Not applicable
Secondary	• The number of clinically significant exacerbations (including exacerbations requiring hospitalization or ED visits) will be analysed using Negative Binomial regression via generalised estimating equations with a covariate of time period (pre-, post-mepolizumab) with follow-up time within each period included as an offset within the model. The exacerbation rates during the pre- and post-treatment with mepolizumab will be presented, including rate ratio comparing of pre- and post-mepolizumab periods and presented with

Endpoint	Statistical Analysis Methods
	corresponding 95% confidence interval.
	A treatment policy strategy will be utilised for the intercurrent event of treatment discontinuation. The period of time for which exacerbation information will be included in the post-mepolizumab period will be from the start of treatment until the week 24 visit, regardless of treatment discontinuation. For those participants with premature study withdrawal, the time period will include from the start of treatment until the date of withdrawal. Missing data (following early withdrawal) will be assumed to be missing at random (MAR) following subject withdrawal from the study.
	Analyses will also be conducted separately using the same analysis model and period definitions for exacerbations requiring hospitalization/ED visits and also exacerbations requiring hospitalization.

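### Exclusion 11 bars prior mepolizumab only when it was given in a study; if users of the marketed product enrol, they can contaminate the pre-mepolizumab reference year

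*Protocol*

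**What the plan says.** Two exclusion criteria in Protocol 5.2 bear on earlier mepolizumab, and SAP 5.2.2 repeats both:

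- Exclusion 11: "Participants who have previously participated in any study of mepolizumab and received Investigational Product (including placebo").
- Exclusion 9: "Participants who have received any monoclonal antibody (other than Xolair) to treat inflammatory disease within 5 half-lives of Visit 1 (screening"). The row for other monoclonal antibodies in Table 2 (Protocol 6.5.3) sets the same washout.

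Exclusion 17 removes "Participants with a known allergy or intolerance to a monoclonal antibody or biologic". No inclusion, exclusion or Treatment Period criterion requires participants to be mepolizumab-naive.

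The study is post-approval. The Synopsis states that "Indian Regulatory authorities have approved marketing of mepolizumab in India for the treatment of severe eosinophilic asthma", and Protocol 6.7 adds that "GSK will not supply mepolizumab post study since the mepolizumab will be available commercially".

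The exacerbation estimand (Protocol 3) is summarised as "Rate ratio comparing events/year during the 24-week follow-up period compared to the 12 months prior to screening". Protocol 9.4.2 fits this with a "covariate of time period (pre-, post-mepolizumab"), and SAP 10.2.1 uses the same two periods. Neither model has a term for earlier biologic use.

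The Schedule of Activities does collect the relevant history at Visit 1: "Therapy history to include a detailed review of prior monoclonal antibodies received for treatment of asthma".

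**The concern.** Exclusion 11 shuts out a person who received placebo in an earlier mepolizumab trial, but not a person treated with the marketed drug. The latter may enter after a washout that is probably shorter than the reference year. For that person the pre-mepolizumab label is wrong for part of the year, and the reference rate may reflect earlier treatment or its withdrawal.

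What is at stake is the reading of a secondary pre/post comparison that has no concurrent control and so depends entirely on its reference period. For the primary endpoint, systemic and injection-site reactions would be counted in a mixture of first-exposed and re-exposed people, and no planned output separates them.

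**Working it through.** **Plan's own figures.** Table 3 gives 0.8673 for at least one event at risk 0.02 with n = 100. Recomputed: 1 − 0.98^100 = 0.8674. Screening: 100/(1 − 0.35) = 153.8, so 154. Both reproduce, and neither depends on this point.

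**When is the washout shorter than the reference year?** Five half-lives are under 365 days when the half-life is under 365/5 = 73 days. The documents do not state the half-life. Three figures in them can serve as rough proxies for the washout, and none is a half-life:

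- at least 90 days of monitoring after an overdose (Protocol 8.4);
- 16 weeks, or 112 days, of contraception after the last dose (Protocol 5.1);
- 130 days, the omalizumab washout (exclusion 8), used here only as a longer illustrative value.

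**Largest on-drug share of the reference year**, e = (365 − washout)/365:

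- 90 days: 275/365 = 0.753
- 112 days: 253/365 = 0.693
- 130 days: 235/365 = 0.644

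**Effect on the rate ratio.** Let r be the true on/off ratio and f the share of prior users, with the same off-drug rate in everyone. A naive participant has reference rate 1 and a prior user 1 − e(1 − r), so the observed ratio is r / (1 − f·e·(1 − r)). With r = 0.50 (assumed):

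| f (assumed) | washout 130 days | washout 90 days |
|---|---|---|
| 10% | 0.5/0.968 = 0.517 | 0.5/0.962 = 0.520 |
| 20% | 0.5/0.936 = 0.534 | 0.5/0.925 = 0.541 |
| 30% | 0.5/0.903 = 0.553 | 0.5/0.887 = 0.564 |

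These are maxima for dosing throughout the reference year up to the washout, with no effect counted after the last dose. If carry-over filled the whole year (e = 1), 10% and 20% would give 0.5/0.95 = 0.526 and 0.5/0.90 = 0.556. A rebound after stopping would raise the reference rate and push the ratio down instead.

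**Scale against sampling error.** Assume 100 participants, 1 to 3 events a year before treatment, r = 0.50 and independent Poisson counts.

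- At 1 a year: 100 events before and 100 × 168/365.25 × 0.5 = 23 after. The standard error of the log ratio is √(1/100 + 1/23) = 0.231, giving a 95% interval of 0.32 to 0.79.
- At 3 a year: 300 and 69 events, standard error 0.134, interval 0.39 to 0.65.

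**Reactions.** Take a naive risk p = 0.02 and a risk q in prior users. The chance of at least one case is 1 − (1 − p)^(100(1−f)) × (1 − q)^(100f).

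- q = 0 (extreme): 0.838 at f = 10% and 0.801 at f = 20%, against 0.867 with no prior users.
- q = 0.01: 0.853 and 0.838.
- If re-exposure raised the risk, the shift would reverse.

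**The case against.** Nothing in the documents shows that any commercial user enrols, and the shares above have no source; the number may be zero. That stands, and it is why the point is conditional.

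Other filters exist. Inclusion 5 requires a physician to judge mepolizumab suitable. Inclusion 4 requires raised eosinophils, which the drug lowers. Both are partial: inclusion 4a accepts a count of 300 cells/µL or more from any time in the previous 12 months, and no minimum number of prior-year exacerbations is required.

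The shift is small, lies well inside the illustrative intervals and mainly understates benefit, on a secondary endpoint with no hypothesis test (Protocol 9.1). This also stands, and it limits the importance of the point rather than its validity.

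Prior exposure is partly visible already, since SAP 9.3 summarises asthma medications by class and period and lists them by subject. What is missing is any exacerbation or reaction result separated by it.

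A reader might go further and infer three things that the documents do not support:

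- **That reaction incidence is biased downward.** Exclusion 17 would select people without known intolerance, but re-exposing sensitised people could act the other way. The estimand population is also not restricted to first exposure.
- **That the antibody results are compromised.** A Week 0 sample is taken, and SAP Table 14.3.5.3 reports treatment-emergent results separately.
- **That the 130-day omalizumab washout creates the same problem.** An omalizumab user can be mepolizumab-naive, so the period label is right, and rewording exclusion 11 would not touch that case.

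**Conclusion.** The gap in the criteria is real, and no other section of either document closes it. Its effect is contingent: it can contaminate the reference rate only if prior commercial users enrol. It would be too strong to say that the comparison is contaminated.

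Under the assumptions shown (washout 90 to 130 days, true ratio 0.50, no carry-over or rebound), 10 to 20% prior users move the ratio to at most about 0.52 to 0.54, mainly toward no effect. The direction for reactions is uncertain. The half-life, the share of prior users and the true ratio are all assumptions. This is a cheap improvement to make, not a flaw that undermines the study.

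**What to change.** 1. If recruitment is still open, reword exclusion 11 to cover mepolizumab received from any source, not only as investigational product in a study. The cost is one line by amendment, and a few prior commercial users become ineligible.
2. In either case, before database lock, use the prior-antibody history taken at Visit 1 to flag participants with mepolizumab before screening, and report how many there are.
3. If there are any, repeat the exacerbation rate ratio and the systemic and local injection-site reaction tables without them, as a sensitivity analysis specified in the SAP.

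Steps 2 and 3 need one derived flag and reruns of planned tables, with no new data collection. The 100 participants, the 154 to be screened and Table 3 are unchanged. If the count is zero, one sentence in the study report settles the matter.
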